5.2. Exclusion criteria

The following exclusion criteria apply:

1. Women: Pregnant, lactating or <6 months post partum
2. Episodic or Chronic Migraine according to the diagnostic criteria listed in ICHD-III beta (2013) section 1, migraine 1, having two or more attacks per month.
3. Change in any medication acting on the central nervous system (CNS) within 28 days before start of the study or during the study
4. Severe depression i.e. having a Beck Depression Inventory-Fast Screen (BDI-FS) score >12
5. Botox injection within 4 months before baseline or during the study.
6. Psychiatric disorders that could interfere with study participation: bipolar disorder, psychotic disorders and dementia.
7. Suicidal behavior and/or ideation i.e. having a Columbia Suicide Severity Rating Scale (C-SSRS) score ≥ 4 during the preceding 2 years
8. Patients currently taking any opioid medication
9. Patients currently taking medically prescribed marijuana
10. Current or history during the preceding year of alcohol or substance abuse including marijuana
11. Intolerance to supraorbital neurostimulation that makes the treatment not applicable (test of nociceptive threshold with specific Cefaly program)
12. Widespread rheumatic diseases (other than FM), evidence of inflammatory rheumatic disease
13. Any unstable medical condition in the judgment of the investigator that would interfere with study participation or study assessments.
14. Implanted active metal or electrical devices in the head
15. Cardiac pacemaker or implanted or wearable defibrillator

6. Medical device and treatment

6.1. Device description

The CEFALY® is a small, portable product, which is meant to be worn on the forehead by attachment to a self-adhesive electrode. Two 1.5V AAA batteries provide power to the CEFALY® device. The CEFALY® generates very precise electrical impulses that permit stimulation of the nerve fibers. The device acts by stimulation of the upper branch of the trigeminal nerve.

The device has been approved by the FDA as a class II therapeutic device indicated for the prophylactic treatment of episodic migraine in patients 18 years of age or older.

The CEFALY® device (Figure 2) is comprised of the following specifications:

- Dimensions: 163 mm x 170 mm x 40 mm.
- Weight: 30 g.

Figure 2 - CEFALY® device

The device is connected to the body via a self-adhesive electrode (Figure 3) applied on the forehead. The patient may use the device through sessions of 20 minutes. The CEFALY® electrode is 94 mm long and 30 mm high. It makes the interface between the device and the skin. It's a multiuse electrode designed to be used 20 times.

Figure 3 - CEFALY® electrode

6.2. Device technology

The CEFALY® is an external cranial neurostimulator designed for supraorbital neurostimulation (also known as external trigeminal nerve stimulation: e-TNS). Trigeminal nerve stimulation induces a sedative effect on the central nervous system.

The CEFALY® generates electrical impulses that are transmitted transcutaneously via a bipolar self-adhesive electrode placed on the forehead.

The CEFALY® operates on direct electrical energy, which is output from two 1.5V AAA batteries.

The CEFALY® delivers electrical energy in the form of rectangular biphasic pulses. The intensity is increasing linearly to reach a maximum of 16 mA after 14 minutes (and then stays constant for 6 minutes). The pulse frequency is 60 Hz. The pulse width is 250 μ s.

If the user feels that the intensity becomes too high, a simple pressure on the button will stabilize the intensity for the rest of the session.

The supraorbital electrode is designed in order to cover both sides of the supratrochlearis and supraorbitalis nerves, which are branches of the trigeminal nerve (Figure 4).

The electrical impulses generated by the CEFALY® device are transmitted transcutaneously via the supraorbital electrode to excite (trigger action potentials) the supratrochlearis and supraorbitalis nerves. Supratrochlearis and supraorbitalis (or supratrochlear and supraorbital) nerves belong to the upper branch of the trigeminal nerve (V1). Therefore the supraorbital neurostimulation is also known as external trigeminal nerve stimulation.

[figure not shown]

Figure 4 - The electrode placed on the forehead covers the supratrochlearis and supraorbitalis nerves

6.3. Mechanism of action

CEFALY® device generates electrical impulses. Electrical impulses get out of the device via 2 metallic contacts. Contacts are in connection with 2 conductive areas on the self-adhesive electrode. The self-adhesive electrode is applied on the forehead. Therefore electrical impulses generated by the CEFALY® device are running through the metallic contacts then through the electrode in order to carry out excitation on the nerve fibers just located under the forehead skin i.e. supratrochlearis and supraorbitalis (or supratrochlear and supraorbital) nerves which belong to the trigeminal nerve. Consequently electrical impulses generated by the CEFALY® trigger signals (action potentials) on supratrochlear and supraorbital nerves or trigeminal nerve. Repetitive excitation of trigeminal nerve is a neuromodulation of the trigeminal system. Neuromodulation of the trigeminal system induces a sedative effect on the central nervous system and a trigeminal nociceptive threshold modification.

6.4. Use during the trial

The CEFALY® will be used twice a day by the patient. The patients should have at least two sessions of stimulation per day, roughly at the same time of the day everyday (morning and evening). A complete treatment session lasts 20 minutes. The patient should therefore use the device 40 minutes a day.

The device contains a system that records the usage statistics (compliance). For each patient it will be possible to know how much time the device has been activated and at what intensity on average the patient has been stimulated.

6.5. Medication during the trial

- Medication acting on the CNS: cannot be changed within 28 days before start of the study or during the study.
- Botox injection: no injection within 4 months before start of the study or during the study

- Opioid medication: forbidden
- Marijuana: forbidden

6.6. Device provisioning

The promoter will deliver the devices directly to the investigators.

The patient will receive the device at the baseline visit and will return it at the end of the 12-week treatment period during the final visit.

7. Practical study modalities

7.1. Measures

The outcome measures taken in the study are all based on self-assessment questionnaires. The following will be used:

- FIQR: evaluation of the impact and the severity of FM symptoms.
- EQ-5D-3L: evaluation of the general quality of life.
- PROMIS for depression, fatigue, and sleep.
- MASQ: assessment of the self-perception of cognitive difficulties.
- PGIC: assessment of the patient perception of change induced by the treatment.

In order to evaluate the modification of pain level from baseline to 4-week treatment and to 12-week treatment, the item of the FIQR related to pain will be used, i.e. numeric rating scale (NRS) scoring the pain between 0 and 10.

During the screening visit, the following tests will be performed to evaluate the exclusion criteria 4 and 7, respectively:

- Beck Depression Inventory-Fast Screen (BDI-FS);
- Columbia Suicide Severity Rating Scale (C-SSRS).

The following table depicts at which visit the various questionnaires are completed.

	Visit 1 Screening	Visit 2 Baseline	Visit 3 Intermediate assessment (4-week treatment)	Visit 4 Final assessment (12-week treatment)
FIQR	● (*)	●	●	●
EQ-5D-3L		●	●	●
PROMIS		●	●	●
MASQ		●	●	●
PGIC			●	●
BDI-FS	●			
C-SSRS	●			

(*) Only the item of the FIQR related to pain.

7.2. Calendar

The study is foreseen to start in September / October 2015 and to be finished by May 31 2016.

8. Data management and statistics

8.1. Data management

The data will be included in the case report form (CRF) that will be provided to the promoter anonymously, using a numbering system.

8.2. Statistics

8.2.1. Sample size

The number of subjects to recruit in the study (50 patients) is estimated to be sufficient for analysis.

8.2.2. Statistical methods

- All relevant general, safety and efficacy data will be descriptively summarized at each time point.
- Continuous data will be summarized by the number of subjects (N), the arithmetic mean, the standard deviation, the coefficient of variation as a percentage (CV%), the median, the inter-quartile range, the minimum and the maximum value.
- Categorical data will be summarized by absolute (N) and relative (%) frequency tables.
- Where considered as relevant, the study data will also be graphically depicted.
- Results analysis will be carry out on a per protocol basis, i.e. on $\geq 50\%$ compliant patients; sub-analysis will be performed as well on an intention to treat basis, i.e. including all subjects who used the study device at least once. For each patient, the average outcome will be calculated before and after the treatment period on all data available, without any imputation of missing data.

9. Management of adverse events

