4.2. Experimental protocol

Patient diagnosed with FM will be screened for study eligibility. Eligible patients will be scheduled for the baseline visit (enrollment visit) that will take place within a maximum of 4 weeks after the screening visit. At the baseline visit, the patients will be given a CEFALY® device together with the necessary accessories for a 12-week treatment period. Outcome measures will be administered at the baseline visit, after 4 weeks of treatment and at the end of the 12-week treatment period. The overall study flow is illustrated in Figure 1.

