4.2.3. Treatment period – intermediate and final visits

During 12 weeks, patients will apply the CEFALY® twice a day, roughly at the same time of the day everyday (morning and evening) for a complete treatment session of 20 minutes. Compliance will be analyzed afterwards using a built-in recording system. An intermediate visit will be scheduled after 4 weeks of treatment (between minimum 4 weeks and maximum 6 weeks) (Visit 3). The patient will complete the visit questionnaires to assess efficacy of the treatment, and report possible side effects and adverse events regardless of possible relationship to the device. A final visit will occur after the 12 weeks of treatment (between minimum 12 weeks and maximum 14 weeks) (Visit 4) to collect the

CEFALY® device and complete visit questionnaires to assess efficacy as well as possible side effects and adverse events reported regardless of possible relationship to the CEFALY® device.

[figure not shown]

Figure 1 - Study flowchart

5. Subjects

The study will include 50 men or women.

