9.7. Notification of pregnancy to the promoter

The CEFALY® device is perfectly safe for pregnant women. However, pregnancy causes many physiologic changes that can interfere with the FM assessment.

If a pregnancy is suspected during the study, the subject should notify the result of the pregnancy test. If the pregnancy is confirmed, it is a drop out and the subject's data are excluded from the analysis.

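### The lead efficacy result is restricted to patients who turn out to be at least 50% compliant; the set of all device users should lead instead

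*Combined protocol and SAP*

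**What the plan says.** Section 8.2.2 (Statistical methods) sets the order of the analyses. First, "Results analysis will be carry out on a per protocol basis", defined as patients with at least 50% compliance. Then a "sub-analysis will be performed as well on an intention to treat basis, i.e. including all subjects who used the study device at least once". The same bullet says averages before and after treatment are taken "on all data available, without any imputation of missing data"; that sentence covers both sets.

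Membership of the lead set is settled after treatment. Section 4.2.3 says "Compliance will be analyzed afterwards using a built-in recording system". Section 6.4 gives the expected use ("The patient should therefore use the device 40 minutes a day") and what the recorder offers ("For each patient it will be possible to know how much time the device has been activated", plus average intensity). Section 8.2.2 does not give the unit or the denominator of the 50%.

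Outcomes are collected "at the baseline visit, after 4 weeks of treatment and at the end of the 12-week treatment period" (section 4.2), with no condition tied to device use. Section 9.7 adds another exclusion after enrolment: when a pregnancy is confirmed, the subject's "data are excluded from the analysis".

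No section names a different lead set for the two primary outcomes in section 3 (pain and FIQR total, baseline to week 12), adjusts for selection by compliance, or plans a sensitivity analysis for missing data.

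**The concern.** A patient enters or leaves the lead set according to how much he or she used the device once treatment had begun. Use can depend on response and tolerability: treatment takes 40 minutes a day for 12 weeks, and section 9.4 lists skin irritation, headache after the session and fatigue as expected events. Fatigue is also a symptom of the disease and one of the outcomes. A patient who gains little or feels worse may use the device less and so drop out of the headline figure. The outcomes are self-reported, and there is no control arm in which similar selection might partly cancel.

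The introductory section says the pilot is meant to give preliminary efficacy data and to set group sizes for later controlled trials. The headline would describe patients who kept using the device rather than all who started. The planned all-user analysis is not a full safeguard, because without week-12 data from non-compliers it drifts toward the compliant-only result.

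**Working it through.** **The plan's own figure.** The only number in section 8.2.1 is 50 patients, with no power, effect size, SD or dropout behind it. It cannot be reproduced, and this point does not depend on it.

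**Size of the gap.** Let q be the share of treated patients who are non-compliant, M_c and M_n the mean improvements in compliant and non-compliant patients, and d = M_c − M_n. Then

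compliant mean − all-treated mean = M_c − [(1 − q)M_c + qM_n] = q × d.

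This holds for any distribution. The documents give neither q nor d, so both are assumed:

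| d (pain points) | gap at q = 20% | gap at q = 40% |
|---|---|---|
| −0.5 | −0.10 | −0.20 |
| 0 | 0 | 0 |
| 0.5 | 0.10 | 0.20 |
| 1.0 | 0.20 | 0.40 |
| 1.5 | 0.30 | 0.60 |

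**Cross-check.** Suppose use and improvement are bivariate normal with correlation r. The gap is then r × SD × φ(z_q)/(1 − q), and the factor φ(z_q)/(1 − q) is 0.350, 0.497 and 0.644 for q = 0.2, 0.3 and 0.4. With an assumed SD of 2.2 for pain change:

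- r = 0.2 gives 0.15, 0.22, 0.28
- r = 0.4 gives 0.31, 0.44, 0.57
- r = −0.2 gives −0.15, −0.22, −0.28

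Dividing by q, r = 0.2 corresponds to d of 0.71 to 0.77 and r = 0.4 to d of 1.42 to 1.54, so the table covers this range. For FIQR total with an assumed SD of 18, r = 0.2 to 0.4 gives 1.3 to 4.6 points, and r = −0.2 gives −1.3 to −2.3. For scale, the standard error of mean pain change with 35 patients is 2.2/√35 = 0.37.

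**What the all-user sub-analysis recovers.** Assume 50 treated: 35 compliant, all with week-12 data and mean improvement 1.7; and 15 non-compliant, of whom 7 attend visit 4 with mean 0.7 and 8 have no week-12 data.

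- Compliant only: 1.70
- All users, available data: (35 × 1.7 + 7 × 0.7)/42 = 1.53
- All treated, if the 8 resemble the 7: (35 × 1.7 + 15 × 0.7)/50 = 1.40
- All treated, no change assigned to the 8: (35 × 1.7 + 7 × 0.7)/50 = 1.29

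The compliant-only gap is 1.70 − 1.40 = 0.30, which equals 0.3 × 1.0. If m of the 15 non-compliers attend, the gap left in the available-data mean is d × [35/(35 + m) − 0.70]. This is 0.175d, 0.133d and 0 for m = 5, 7 and 15, so changing the lead set removes 42%, 56% and 100% of the gap. With m = 0 the two sets give the same mean.

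**Possible consequence for later trials.** If planners scaled their target effect to the pilot mean with the SD unchanged, group size would vary as 1/effect². Using 1.70 where 1.40 is right gives (1.40/1.70)² = 0.68, so groups would be about 32% too small.

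**The 50% rule.** Planned use is 12 × 7 × 2 = 168 sessions, or 12 × 7 × 40 = 3360 minutes; half is 84 sessions or 1680 minutes. A patient with full use who stops after 3 weeks has 3 × 7 × 40 = 840 minutes. That is 25% of planned use (outside the lead set) but 100% of the use due until stopping (inside it).

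**The case against.** The strongest reply is that the bias is conditional and nothing in the documents shows it will occur. Every input above is assumed, the sign is not established, and with d of 0.5 to 1.0 most of the gaps lie below the standard error of 0.37. The plan already reports both sets, and the analysis is descriptive, so no test or success rule depends on which comes first. A no-change analysis goes against the plan's choice not to impute, and in the example it errs low by 0.11 (1.29 against 1.40) while available data err high by 0.13 (1.53 against 1.40). Finally, the all-user set still leaves out anyone given the device who never used it.

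Much of this is fair. The size is unknown, no type I error is at stake, and the no-change result is a conservative bound rather than a correction. Never-users do remain outside the set as section 8.2.2 defines it. But comparison with the standard error does not settle the matter: selection bias is systematic and more patients would not reduce it. Reporting both sets leaves the selected one in the lead, and the second set is only as informative as the week-12 data from non-compliers.

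**Conclusion.** The concern holds. Section 8.2.2 bases the lead result on a set chosen by device use after treatment starts and ranks all users second. If lower benefit goes with lower use, the lead mean change is too favourable by q × d: 0.10 to 0.60 pain points for q of 20% to 40% and d of 0.5 to 1.5, all assumed. If d is zero there is no gap, and if d is negative the lead result is too pessimistic. What is certain is how the sets are defined and the identity; the direction and size in this trial are not known. In a descriptive pilot this should be fixed but does not invalidate the study. The undefined denominator and the pregnancy exclusion are secondary gaps, and the conclusion does not rest on them.

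**What to change.** In section 8.2.2:

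1. Make all subjects with any device use the primary set for the 12-week change in pain and FIQR total, and keep the at-least-50% compliant set as supportive. State how the exclusion in section 9.7 applies to each set, and report the number excluded. Also report how many patients received a device and never used it.
2. Report how many treated patients lack week-12 data, with reasons. Add one sensitivity analysis that assigns them no change from baseline for pain and FIQR total, and non-response for FM30 and FM20. Label it conservative and read it for its mean, not its SD.
3. Before data review, fix the unit and the planned 12-week denominator of the 50% rule, for example 1680 of 3360 minutes, or 84 of 168 sessions, so that early stoppers are counted against planned use. Section 6.4 describes recorded activation time rather than session counts, so minutes look the safer unit. State how use after week 12 is treated, since visit 4 may fall as late as week 14.

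The cost is SAP wording, a short table and one small extra analysis; both sets are already planned. The headline change will probably be smaller.

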Fibromyalgia (FM) is a chronic pain syndrome with characteristic symptoms of fatigue, sleep disturbance, mood problems and cognitive complaints. Recent research suggests that the central nervous system (CNS) plays a major role in these symptoms in part through central sensitization [1,2]. Current medications for the treatment of FM have limited efficacy and are associated with side effects for most patients. Furthermore, polypharmacy is common in patients with FM, which potentially increases the side effect burden of treatment. e-TNS (external trigeminal nerve stimulation) with the CEFALY® device produces a sedative effect [3] and has proven its efficacy as a prophylactic treatment for episodic migraine [4,5]. The device is FDA-approved for the prevention of frequent episodic migraine and is very safe, with less than 5% of reported adverse events that are all minor and fully reversible. Besides its indication for migraine, e-TNS CEFALY® device shows several actions on the CNS that could support its use in FM: it produces a sedative effect during the session, pilot trials reported improvement in depression [6], and migraine patients frequently report improved sleep and less fatigue. Therefore e-TNS with CEFALY® might help to improve symptoms of FM and make available a new valuable therapeutic treatment for FM.

Prior to conducting a randomized sham controlled clinical trial to investigate the efficacy and safety of e-TNS with the CEFALY® device in FM, a pilot open trial is needed to collect preliminary data on efficacy and safety and to establish the group sizes for the subsequent controlled trials.

2. Study objective

The main objective of this clinical pilot trial is to evaluate the use of the CEFALY® neurostimulator as a therapeutic treatment for FM.

3. Study outcomes

Primary outcomes:

- Mean pain intensity between baseline and 12 weeks endpoint
- Fibromyalgia Impact Questionnaire-revised (FIQR) total score between baseline and 12 weeks endpoint

Secondary outcomes:

- Mean pain intensity between baseline and 4 weeks visit
- FIQR total score between baseline and 4 weeks visit
- Patient Global Impression of Change (PGIC) at 4 weeks visit and at 12 weeks endpoint
- EQ-5D-3L between baseline and 4 weeks visit; and between baseline and 12 weeks endpoint
- Patient Reported Outcomes Measurement Information System (PROMIS) measures for depression, fatigue and sleep between baseline and 4 weeks visit; and between baseline and 12 weeks endpoint

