9.5. AE collection

The patients are instructed to report all AEs to the investigator. AEs will be registered daily by the subject in the corresponding form. This form will be returned by the subject at the intermediate visit and at the end of the study and will be analyzed by the investigator who will document it in the CRF.

All AEs will be collected in the CRF, specifying:

- Their nature
- Start date and duration
- Causality (according to investigator's opinion)
- Countermeasures and results

If the AE is a SAE, the promoter should be notified as soon as possible.

9.6. Investigator's responsibility with respect to a SAE.

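### Section 8.2.2 names no safety set, so read literally its lead adverse-event summary covers only patients at least 50% compliant and omits low users who stopped because of a side effect

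*Combined protocol and SAP*

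**What the plan says.** The introduction makes safety one of the reasons for the study: "a pilot open trial is needed to collect preliminary data on efficacy and safety". Section 3 then lists only efficacy outcomes.

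Section 8.2.2 holds the whole statistical plan. Its first bullet covers both kinds of data: "All relevant general, safety and efficacy data will be descriptively summarized at each time point". Its last bullet sets the analysis populations without limiting them to any type of outcome: "Results analysis will be carry out on a per protocol basis", defined as patients at least 50% compliant. It then adds that a "sub-analysis will be performed as well on an intention to treat basis, i.e. including all subjects who used the study device at least once". The same bullet goes on to describe averaging each patient's outcome before and after treatment.

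On compliance, section 4.2.3 says: "Compliance will be analyzed afterwards using a built-in recording system". Neither section gives the denominator for the 50%.

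On AEs, section 9.5 says "All AEs will be collected in the CRF, specifying" and lists the details to record. It names no population or denominator for reporting them.

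**The concern.** Compliance is measured after treatment has started and depends partly on how well the device is tolerated. The AEs expected in section 9.4 (skin irritation, gel allergy, post-session headache, fatigue) are plausible reasons to use the device less or to stop. A summary restricted to patients above a compliance threshold is therefore partly restricted to patients who tolerated the device. Any resulting error in the AE rate would be expected to favour the device.

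This matters because the pilot is meant to prepare a sham-controlled trial. How many patients stop because of a side effect is a planning input for that trial, and it is the figure most affected by the choice of set. The point concerns the AE summaries only, not the pain or FIQR analyses.

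**Working it through.** **1. Does any text separate safety from the rule?** The plan states no safety calculation to reproduce, so the first check is a reading of the relevant sections.

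- Section 8.2.2, first bullet: safety and efficacy data are summarised together; no population is given.
- Section 8.2.2, last bullet: the compliant set leads and all users are a sub-analysis; no outcome type is exempted.
- Section 3: no safety outcome, and so no safety population.
- Section 9.5: all AEs are collected; no analysis set is named.
- Section 9.7: data from confirmed pregnancies leave the analysis, again with no separate provision for safety data.

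The only population rule that could apply to AEs is the one in the last bullet of 8.2.2.

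**2. Where does the 50% threshold fall?** Inputs: 2 sessions of 20 minutes a day (sections 4.2.3 and 6.4) and 12 weeks = 84 days (section 4.2.3). Assumption: compliance is counted against all planned sessions.

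- Planned sessions: 2 × 84 = 168 (168 × 20 = 3,360 minutes).
- Threshold: 0.5 × 168 = 84 sessions (1,680 minutes).
- Day on which it is reached = 84 ÷ sessions per day: day 42 at 2 a day, day 56 at 1.5 a day, day 84 at 1 a day.

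A full user who stops before day 42 is outside the lead set; a full user who stops later stays in. Less regular users can stop later than day 42 and still be outside.

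If compliance were instead counted over time on treatment, a full user who stops early would stay in. A patient who cuts down to fewer than 1 session a day over the 84 days would be below 50% under either denominator.

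**3. What would the two sets show?** Assumptions: all 50 planned patients use the device at least once, and *s* of them stop below the threshold because of an AE; nobody else is excluded. All users show *s*/50. The compliant set shows 0/(50 − *s*), with exact (Clopper-Pearson) upper 95% limit 1 − 0.025^(1/(50 − *s*)).

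| *s* (assumed) | All users | Compliant set | Upper 95% limit | Limit below all-user rate? |
|---|---|---|---|---|
| 2 | 4% | 0/48 | 7.4% | no |
| 3 | 6% | 0/47 | 7.5% | no |
| 4 | 8% | 0/46 | 7.7% | yes, just |
| 5 | 10% | 0/45 | 7.9% | yes |
| 10 | 20% | 0/40 | 8.8% | yes |

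The exact 95% interval in all users is 3.3% to 21.8% for 5/50 and 10.0% to 33.7% for 10/50.

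The zeros follow from the definition, because the early stoppers have been removed before counting. The rate of any AE is less extreme. If 5 patients stop early for an AE and 5 others have an AE but continue (both assumed), all users show 10/50 = 20% and the compliant set shows 5/45 = 11.1%.

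**The case against.** The strongest reply is that the rule was written for efficacy. No sentence assigns AE tables to the per-protocol set. The sentence that follows the rule averages outcomes before and after treatment, which does not fit AEs, and section 7.1 describes the outcome measures as self-assessment questionnaires. The one sentence that names safety sets no compliance condition. This stands as evidence of intent. It does not settle the text: the rule is unqualified, and an analyst who departs from it for safety would be choosing the safety denominator without a prespecified basis.

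Second, nothing is lost. AEs are recorded daily and entered in the CRF (section 9.5), every SAE is declared whatever its cause (section 9.6.2), and an analysis of all users is already planned. This also stands. The issue is which of two planned sets leads.

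Third, the effect may be small. The introduction cites less than 5% adverse events, all minor and reversible; section 9.4 gives 0.52% for headache and 1 in 1,000 for gel allergy. Intolerant patients are screened out (section 5.2, criterion 11), and users can hold the intensity down (section 6.2). Less than 5% of 50 is at most 2 patients, and at 2 the compliant-set limit still covers the all-user rate. This is a fair limit on size. These figures come from earlier use of the device, however, and may not carry over to fibromyalgia.

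A reader might infer more: that the plan expressly filters AEs by compliance, that no stopping for an AE can appear in the lead set, or that the lead result is bound to contradict the all-user rate. The documents support none of these. The first is a literal reading of a general rule, the second fails for patients who stop above the threshold, and the third depends on how many stop.

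**Conclusion.** The point holds as a fault in how the analysis sets are ranked for safety. On the literal text, the lead AE summary is conditioned on a post-treatment variable that depends on tolerability, and the set suited to safety is relegated to a sub-analysis. The direction favours the device. The size is unknown in advance: with 2 or 3 early AE stoppers among 50 the two sets remain statistically compatible, and from about 4 upward the compliant-set limit falls below the all-user rate.

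This rests on three things: the literal reading of 8.2.2, a 168-session denominator for the day-42 cut-off, and assumed numbers of stoppers. The need for clarification survives without the last two, because no section says which patients the safety summaries cover. It should be corrected, but it does not undermine the study.

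**What to change.** In section 8.2.2, limit the per-protocol rule to efficacy outcomes. State that all safety summaries, including the number of patients who stop because of an AE, use every subject with at least one use of the device. That set is already defined there.

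The cost is a sentence or two, with no extra patients or visits and no change to the efficacy analysis. The number stopping for an AE requires the reason for stopping to be recorded. Section 9.5 does not list it explicitly, so the CRF should be checked. The reported AE rate may become slightly less favourable.

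Stating the compliance denominator would also help, although AE reporting would no longer depend on it. Formal safety outcomes in section 3, event rates per recorded session, and collecting the AE form when a patient stops are optional. The last is a change in trial conduct, and the correction does not depend on any of them.
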